9 EXPLORATORY STATISTICAL ANALYSES

9.1 Exploratory Analyses

9.1.1 Overview of Planned Exploratory Analyses

The exploratory analyses will be based on different populations depending on what the endpoint is.

Table 16 provides an overview of the planned exploratory analyses, with further details of data displays being presented in [Appendix 13: List of Data Displays](#).

Table 16 Overview of Planned Exploratory Analyses

Endpoint	Absolute							
	Stats Analysis			Summary		Individual		
	T	F	L	T	F	F	L	
TNSS								
WM TNSS by Week	Y		Y		Y		Y	
WM Individual Components of TNSS by Week	C		C		C		C	

NOTES :

- T = Table, F = Figure, L = Listing, Y = Yes display generated, C=Display conditional on other results.
- Stats Analysis = Represents TFL related to any formal statistical analyses (i.e. modelling) conducted.
- Summary = Represents TFL related to any summaries (i.e. descriptive statistics) of the observed raw data.
- Individual = Represents FL related to any displays of individual subject observed raw data.

Intradermal Allergen Challenge	Log Untransformed											
	Absolute						Change from Baseline					
	Stats Analysis			Summary		Individual	Stats Analysis			Summary		Individual
	T	F	L	T	F	F	L	T	F	L	T	F
Mean Diameter Early Phase Response (15m)												
Wheal/Flare data	C	C	C	Y			Y			Y	Y	Y
Mean Diameter Late Phase Response (6h)												
Wheal/Flare data	C	C	C	Y			Y			Y	Y	Y

NOTES :

- T = Table, F = Figure, L = Listing, Y = Yes display generated, C=Display conditional on other results.
- Stats Analysis = Represents TFL related to any formal statistical analyses (i.e. modelling) conducted.
- Summary = Represents TFL related to any summaries (descriptive statistics) of the observed raw data.
- Individual = Represents FL related to any displays of individual subject observed raw data.

Weighted Mean TNSS

The weighted means of the TNSS values (AM and PM values combined into an overall daily score prior to deriving WM) will be derived for each diary card week. They will be analysed using a similar model to FeNO (Section [8.4.2.3.5](#)) except the response is not anticipated to require any transformation, so the model should be modified to examine differences and not ratios and to account for the additional Follow Up Visit timepoints.

Baseline would be the Day 1 AM TNSS value and Visit would be the week (of each weighted mean).

Conditional on the above output the following may be attempted (and would be assigned the next available output number):

Modelling repeated as above for AM and PM weighted means (derived separately; with Baseline being Day 1 AM TNSS in both models)

Each individual TNSS component may have weekly Weighted Means determined and modelled (for overall and separate AM and PM endpoints; with baseline term being the respective TNSS component from Day 1 AM).

Intradermal Allergen Challenge

Summary statistics for the absolute and change from baseline values will be produced, along with a Figure of the change from baseline values. Further Statistical modelling is conditional on i) review of these summary outputs and ii) other study results / outcomes and would be similar to the other repeated measures models fitted in this study (main aim to compare the treatment effects within each visit). Further details of any statistical modelling would be provided in the CPSR.

Note: Intradermal Allergen Challenge test procedures will not be performed on subjects if the allergen manufacturer is “Allergopharma” (i.e. no data for those individuals). This manufacturer is being used as a solution in response to anticipated supply issues during the clinical study, and may impact on a number of individuals. If the proportion of missing data is large then statistical modelling may not take place.

11 APPENDICES

Section	Appendix
RAP Section 4 : Analysis Populations	
Section 11.1	Appendix 1 : Protocol Deviation Management and Definitions for Per Protocol Population
RAP Section 5 : General Considerations for Data Analyses & Data Handling Conventions	
Section 11.2	Appendix 2 : Assessment Windows
Section 11.3	Appendix 3 : Treatment States & Phases
Section 11.4	Appendix 4 : Data Display Standards & Handling Conventions 
 • Study Treatment & Sub-group Display Descriptors • Baseline Definitions & Derivations • Reporting Process & Standards
Section 11.5	Appendix 5 : Derived and Transformed Data 
 • General, Study Population & Safety • Efficacy • Pharmacokinetic • Pharmacodynamic and or Biomarkers
Section 11.6	Appendix 6 : Premature Withdrawals & Handling of Missing Data 
 • Premature Withdrawals • Handling of Missing Data
Section 11.7	Appendix 7 : Values of Potential Clinical Importance 
 • Laboratory Values • ECG • Vital Signs
Section 11.8	Appendix 8 : Multicentre Studies
Section 11.9	Appendix 9 : Examination of Covariates and Subgroups
Section 11.10	Appendix 10 : Multiple Comparisons and Multiplicity
Section 11.11	Appendix 11 : Model Checking and Diagnostics for Statistical Analyses
Other RAP Appendices	
Section 11.12	Appendix 12 : Abbreviations & Trade Marks
Section 11.13	Appendix 13 : List of Data Displays
Section 11.14	Appendix 14 : Example Mock Shells for Data Displays (see separate document: RAP-Mock Tables-205540.doc)

11.1 Appendix 1: Protocol Deviation Management and Definitions for Per Protocol Population**11.1.1 Exclusions from Per Protocol Population**

The Protocol Deviation Management Plan (PDMP) contains more detail on the specific items that may cause subjects to be excluded from the per protocol population. In general a subject meeting any of the following criteria is expected to be excluded from the Per Protocol population (as described in the PDMP reviews and decisions will occur on a case by case basis):

Number	Exclusion Description
01	Failure of any inclusion/exclusion criteria, but subject is still enrolled.
02	Subject took short-acting beta-agonist (SABA) more than 2 days per week on average.
03	Subject did not receive all 8 doses of planned medication (Placebo or GSK2245035).
04	Subject did not receive the same allergen dose during study period as that determined at Screening (except for cases where the dose was reduced for safety reasons- in which case the same (reduced) dose must be used at all follow up challenges (otherwise the individual should be excluded)).

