7 PRIMARY STATISTICAL ANALYSES

7.1 Efficacy Analyses

7.1.1 Overview of Planned Efficacy Analyses

The primary efficacy analyses will be based on the PP population, unless otherwise specified. As a potential sensitivity analysis the final primary analysis model structure (derived using the PP population) may also be run using the mITT population (conditional on the PP and mITT populations differing).

Table 5 provides an overview of the planned efficacy analyses, with full details of data displays being presented in [Appendix 13: List of Data Displays](#).

Table 5 Overview of Planned Efficacy Analyses

Endpoint	Absolute							
	Stats Analysis			Summary		Individual		
	T	F	L	T	F	F	L	
LAR								
Min and WM FEV ₁ absolute change from saline at Week 9 (FUV1)	Y	Y	Y	Y	Y	Y	Y	

NOTES :

- T = Table, F = Figure, L = Listing, Y = Yes display generated.
- Stats Analysis = Represents TFL related to any formal statistical analyses (i.e. modelling) conducted.
- Summary = Represents TFL related to any summaries (i.e. descriptive statistics) of the observed raw data.
- Individual = Represents FL related to any displays of individual subject observed raw data.

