7.1.2 Planned Efficacy Statistical Analyses

Primary Statistical Analyses
Endpoint(s)

 • LAR: minimum <change from saline baseline> FEV₁ between 4-10 hours following allergen challenge 1 week after treatment i.e. FUV1. • LAR: weighted mean of <change from saline baseline> FEV₁ between 4-10 hours following allergen challenge 1 week after treatment i.e. FUV1. 
Note: Text in <> added for clarity, since the wording in the protocol and objectives is familiar to clinical experts in the field, but may be confusing given there are also absolute FEV1 values measured at those times too.
 
 • The “raw” data (replicate (absolute) FEV1 values transcribed into the eCRF) require processing before the Primary analysis. Each planned timepoint may be associated with replicate FEV1 values, which need to be condensed down into a single value (giving a single FEV1 value per timepoint per subject; the timepoints determine how the data are condensed, i.e. some timepoints use the minimum of the replicates others use the maximum). In addition the Screening Visit 2 Incremental BAC challenge may also contain additional FEV1 values relating to the selection procedure for the bolus BAC concentration. Such FEV1 values are not used in the statistical analyses (subjects may differ in the amounts of additional FEV1 data to be excluded). Once the single time profile of absolute FEV1 values is available per subject the Saline baseline is subtracted from each to leave a time profile of change from saline baseline FEV1 values. The minimum and weighted means endpoints are derived from this change from saline baseline time profile. Further details are given in Section 11.5.4. • Any transformation of a response variable is also expected to be applied to the corresponding baseline variable. Final decisions on transformations will be based on the observed data and model diagnostics • Any observations with missing model covariates (e.g. baseline) would be excluded from the model fitting process (i.e. also excluding the record from any centering of covariates)
Model Specification

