- If an observation is missing between two non-missing observations, the AUC will be linearly interpolated between the two non-missing values i.e., the subject's profile will be assumed to be linear between the two available values. No imputation will be made if either the first or last observation is missing.
- If the number of missing values is considered to be substantial, or if the data is not considered to be missing at random, a sensitivity analysis will be carried out with respect to methods of handling missing data in the calculation of the weighted mean.
- The weighted mean will be set to missing for the relevant challenge if any of the following occurs:
 - A short-acting inhaled β -agonist is taken within 8 hours at any time prior to the challenge
 - The dose of allergen administered is different to that of the Screening dose. Note that the dose of allergen used during the treatment period may be modified from the total dose received at screening, for safety reasons, at the discretion of the investigator. However, in this case, the modified dose used must be consistent for all follow up visits. [In these cases the baseline will be set to missing.]
 - The weighted mean LAR will be set to missing if the subject took rescue medication prior to the LAR period i.e., between 0 and 4 hours post-saline.
 - If rescue medication is administered during the LAR period prior to the completion of the 10 hour FEV_1 assessment, all FEV_1 values recorded after the administration of rescue medication for that challenge will be set to the last recorded FEV_1 value prior to the administration of rescue medication. The LAR does not have the same natural recovery as the EAR, hence this is the most appropriate derivation for the LAR. The weighted mean LAR will then be calculated as above, using the imputed data set.
 - If the use of rescue medication is widespread and/or appears to follow a trend, appropriate sensitivity analyses to examine the impact of the derivations may be conducted. For example, if a large number of subjects are rescued at around 8 hours, the weighted mean LAR over 4-8 hours may be derived and analysed as a sensitivity analysis. All sensitivity analyses will be documented in the CPSR.
 - There may be other conditions that effect the LAR response. In such situations it may be necessary to set the respective response to missing. Such scenarios will be

LAR and EAR

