identified and documented before unblinding or DBF. Appropriate, sensitivity analyses may be conducted if other situations are noted following unblinding or DBF.
Minimum LAR

 Minimum FEV₁ over 4-10 hrs post-saline challenge will be the minimum value of all the post-saline time points between 4 to 10 hours post-allergen challenge, inclusive of 4 hrs and 10 hrs time points i.e., minimum over 4 hrs, 4.5 hrs, 5 hrs, 5.5 hrs, 6 hrs, 6.5 hrs, 7 hrs, 7.5 hrs, 8 hrs, 8.5 hrs, 9 hrs, 9.5 hrs and 10 hrs. Note that the maximum FEV₁ value at each planned relative time point will be derived, where replicates are taken, for every subject and period, before the minimum values are calculated over the specified time period above. The minimum will be set to missing for the relevant challenge if either of the following occurs: 
 The subject did not receive the correct dose of study medication at any of the 8-weekly visits. A short-acting inhaled β-agonist is taken within 8 hours at any time prior to the challenge. If subject took rescue medication prior to the LAR period i.e. between 0 and 4 hours post-saline administration. The incorrect dose of allergen is administered for the respective BAC. Note that the dose of allergen used during the treatment period may be modified from the total dose received at screening for safety reasons at the discretion of the investigator. However, in this case, the modified dose used must be consistent for all follow up visits. In these cases only the baseline value will be set to missing (essentially removing the subject from any statistical modelling that has the baseline term as a covariate).
There may be other conditions that affect the LAR response. In such situations it may be necessary to set the respective response to missing. Such scenarios will be identified and documented before unblinding. Appropriate, sensitivity analyses may be conducted if other situations are noted following unblinding.
EAR
Weighted Mean EAR

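### Per-protocol exclusion 04 lets a safety dose reduction at week 12 or 20 remove a valid week-9 primary result by default

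*SAP*

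**What the plan says.** SAP 7.1.2 defines both primary endpoints as LAR measures "following allergen challenge 1 week after treatment i.e. FUV1". SAP 7.1.1 sets the population: "The primary efficacy analyses will be based on the PP population, unless otherwise specified". The challenges at FUV2 and FUV3 come about 4 and 12 weeks after the last dose (protocol 4.4).

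SAP 11.1.1 lists the PP exclusions. Item 04 concerns subjects who did not receive the screening-determined allergen dose. It exempts safety reductions on one condition: "the same (reduced) dose must be used at all follow up challenges (otherwise the individual should be excluded". The lead-in makes exclusion a default, "In general a subject meeting any of the following criteria is expected to be excluded from the Per Protocol population", and adds that "reviews and decisions will occur on a case by case basis". It refers to a Protocol Deviation Management Plan that is not among the documents.

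SAP 11.5.4 deals with the same event when deriving the endpoints:
- **Weighted mean LAR:** "The weighted mean will be set to missing for the relevant challenge if any of the following occurs". A dose different from the screening dose is one of the triggers.
- **Minimum LAR:** an incorrect dose voids the value for that challenge. For safety modifications, "only the baseline value will be set to missing (essentially removing the subject from any statistical modelling". The weighted-mean text has the same baseline rule.

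Both parts of 11.5.4 also ask that a modified dose be consistent across follow-up visits.

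On the modified intent-to-treat (mITT) set, SAP 7.1.1 says the primary model "may also be run using the mITT population (conditional on the PP and mITT populations differing".

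**The concern.** Membership of a primary population should not depend on what happens after the primary endpoint has been measured. Consider a subject whose FUV1 challenge used the screening-determined dose and whose dose is first reduced at FUV2 or FUV3. That subject has a correctly obtained FUV1 value, but did not have the same dose at all follow-up challenges. Item 04 acts on the whole subject, so by default the FUV1 value leaves the primary analysis along with the later visits. The per-challenge rules in 11.5.4, taken on their own, would leave it in place.

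The loss may not be random. Reductions are made for safety at the investigator's discretion, so they could follow a strong reaction at FUV1. In that case the exclusion depends on the primary outcome itself. With 20 completers per arm, one or two such exclusions concentrated in one arm are enough to move the estimate.

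A second gap lies next to the first. A subject reduced consistently from FUV1 onward is kept in PP by item 04, but 11.5.4 then sets that subject's baseline to missing, and all three candidate models (M1 to M3) include baseline.

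**Working it through.** **Inputs.** Protocol Table 2, minimum LAR, eight historical studies, with residual variability read as a variance; 18% attenuation; 20 completers per arm; success if the posterior probability of any attenuation exceeds 0.7 (z = 0.5244). The documents give no rate of dose reduction.

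**Reproducing the plan's figure.**
- Placebo mean = −8.4032/8 = −1.050 L.
- Variance weighted by degrees of freedom = 67.469/358.4 = 0.1883, so SD = 0.434 L.
- Active mean = −1.050 × 0.82 = −0.861 L; difference = 0.189 L.
- SE = 0.434 × √(2/20) = 0.137.
- Success = Φ(0.189/0.137 − 0.5244) = 0.80.
- With the unweighted mean variance (0.2329, SD 0.483), success = 0.76.

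The protocol's 78% lies between the two.

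**Exclusion linked to outcome (assumed).** Suppose every FUV1 value below a common cut-off c leads to a later reduction and hence to exclusion, where c is the worst 5%, 10% or 15% point of the placebo distribution. For an arm with mean a, let z = (c − a)/SD and λ = φ(z)/(1 − Φ(z)). Then:
- retained mean = a + SD·λ
- retained variance = SD²(1 + zλ − λ²)
- retained n = 20(1 − Φ(z))
- success = Φ(difference/SE − 0.5244), with SE from the retained SDs and n.

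| Placebo worst | 5% | 10% | 15% |
|---|---|---|---|
| Cut-off (L) | −1.764 | −1.606 | −1.500 |
| Excluded on active | 1.9% | 4.3% | 7.0% |
| Retained mean, placebo / active | −1.003 / −0.841 | −0.966 / −0.820 | −0.931 / −0.798 |
| Retained SD, placebo / active | 0.390 / 0.412 | 0.366 / 0.395 | 0.347 / 0.380 |
| Retained n, placebo / active | 19.0 / 19.6 | 18.0 / 19.1 | 17.0 / 18.6 |
| SE | 0.129 | 0.125 | 0.122 |
| Attenuation | 16.2% | 15.1% | 14.3% |
| Success | 0.77 | 0.74 | 0.71 |

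First column: attenuation = 1 − 0.841/1.003 = 16.2%; success = Φ(0.162/0.129 − 0.5244) = 0.77.

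If only half of the subjects below the cut-off are reduced, attenuation is 17.1/16.8/16.5% and success 0.79/0.78/0.77. For weighted mean LAR (27%, SD 0.360 L), removing all of them gives attenuation of 24.8/23.5/22.6%.

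**Direction.** A simulation of 40,000 trials (20 per arm, SD 0.483, flat prior, success 76% with no exclusions) dropped the strongest FUV1 reactors by assumed count:

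| Dropped | True attenuation | Estimated | Success |
|---|---|---|---|
| 1 placebo | 18% | 14.0% | 66% |
| 2 placebo, 1 active | 18% | 15.4% | 69% |
| 1 placebo, 1 active | 18% | 18.8% | 77% |
| 1 active | 18% | 22.4% | 85% |
| 1 active | 0% | 4.4% | 42% (30% with none dropped) |

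Losing 5 to 10% of subjects at random costs only 1 to 2 points of success.

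**The case against.** The case for leaving the text alone has several parts.

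- **Exclusion is not automatic.** It is expected in general and reviewed case by case, and SAP 4.1 places the deviation review before unblinding and database freeze. This stands, so the documents do not support the inference that such FUV1 values will certainly be deleted. The protection is partial: the sponsor is open, and the unblinded headline snapshot taken after the last FUV1 (SAP 3.2) can precede some FUV2 and FUV3 challenges.
- **mITT coverage is better than 7.1.1 alone suggests.** SAP 8.1.1 says the mITT repeated-measures LAR analysis will be run if PP and mITT differ, and it yields a FUV1 estimate. Table 2.4, Figures 2.6 and 2.7 and Listings 44 and 45 cover FUV1 in mITT at top priority under the same condition. This stands, provided the missing-baseline rule does not reach subjects reduced only later.
- **The rules are not flatly opposed.** SAP 11.5.4 shares item 04's wish for a consistent dose, and protocol 7.3.1 plans one bolus dose for all three follow-up challenges. A first reduction at FUV2 is therefore a real departure. It does not make the FUV1 value invalid.
- **A reader might infer that any safety reduction removes the subject from the primary model.** SAP 7.1.2 and 11.5.4 point to omission when baseline is missing, but SAP 11.6.2.3 allows a missing baseline to be imputed case by case. Certain removal does not follow.
- **The link to outcome is not documented.** A reduction could follow the early response or anaphylaxis rather than the LAR. This stands.
- **A difference between headline and final subject sets is not in itself a defect.** The plan says the headline results will be superseded.

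**Conclusion.** The point holds as a wording fault that should be corrected. By default, item 04 allows a dose change after the primary endpoint to remove a valid FUV1 value from the primary analysis, while 11.5.4 works per challenge. Case-by-case review and the listed mITT outputs keep it from being critical, and the number of subjects affected may be zero.

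The sizes above rest on two assumptions that the documents do not state: that later reductions follow strong FUV1 LAR values, and how often they occur. On those assumptions the loss is modest, about 2 to 4 points of attenuation and 3 to 9 points of success for minimum LAR, and 1 to 3 points of success if only half are reduced. Holding the SD at its untruncated value would give a larger fall, to 0.75/0.71/0.67, but that overstates it because cutting the tail also shrinks the spread.

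A reader might conclude that the bias always runs towards no effect. It does so if the drug works and strong reactions are therefore commoner on placebo. Losses mainly on active inflate the effect, and equal losses leave the difference nearly unchanged.

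**What to change.** In SAP 11.1.1 item 04 and the deviation management plan, judge allergen-dose compliance for the FUV1 primary analysis on the FUV1 challenge only. State that a FUV1 result obtained at the screening-determined dose stays in the PP analysis whatever dose is used at FUV2 or FUV3; later challenges remain subject to the per-challenge rules in 11.5.4.

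Reconcile item 04 with SAP 7.1.2, 11.5.4 and 11.6.2.3 on two questions: whether a subject reduced consistently from FUV1 onward, whom item 04 keeps in PP, is then lost through the missing baseline; and whether the missing-baseline rule reaches subjects reduced only after FUV1.

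The cost is a few sentences, with no extra data or subjects. It is best settled before the headline snapshot, while no unblinded FUV1 result can influence who stays in. No allergen dose or safety rule is proposed here.

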11.2 Appendix 2: Assessment Windows

11.2.1 Definitions of Assessment Windows for Analyses

Data Management are responsible for documenting and implementing the visit windows in this study. If an item is within its visit window it should be transferred to statistics and programming using the corresponding timeslicing key (items that fall outside of the window may be transferred using unscheduled timeslicing keys with the corresponding planned items containing no data). In addition this should also be captured in the protocol deviations dataset. For the purposes of AE, DRE and CRS assignments the algorithms described in Section 11.3.2 should be used.

